13.1.2 Timing of ECG and Sample Collection for PK, ADA, ██████████ and PBMCs

| Assessment | Cycles 1 and 2 | | | | | | | | | | Cycle 3 – Progression | | EOT | Follow up 3 mos after last infusion (±7 days) | |
|----------------------------------|-----------------------|-------------|-----------------------|------------------------|------------------------|-------------------------|-------------------------|---------------------------|-----------------------------|-----------------------------|------------------------------|------------|------------|--|----------------|
| | Day 1 | | | | | Day 2 | Day 3 | Day 5 | Day 8 | Day 15 | Day 1 | | | | |
| | Before start infusion | EOI (±10%)* | 1 hr after EOI (±10%) | 3 hrs after EOI (±10%) | 6 hrs after EOI (±10%) | 24 hrs after EOI (±10%) | 48 hrs after EOI (±10%) | 96 hrs after EOI (±1 day) | 168 hrs after EOI (±2 days) | 336 hrs after EOI (±2 days) | Before start infusion (±10%) | EOI (±10%) | | | |
| PK | X | X | X | X | X | X | X | X | X | X | X | X | X | X | X ¹ |
| ADA ² | X | | | | | | | | | | | | X | X | X ¹ |
| sCD25 | X | | | | | | | | | | | | X | X | |
| ██████████ | ██████████ | | | | ██████████ | ██████████ | | | | | | | ██████████ | ██████████ | |
| PBMC subsets (Study Part 2 only) | X | | | X | | | X | X | X | X | | | | X | |
| ECG | X | X | | X | | X | | | | | X | | X | X | |

Abbreviations: ADA, anti-drug antibody; EOI, end of infusion; EOT, end of treatment; ██████████; hr, hour(s); mos, months; PK, pharmacokinetics; ██████████ PBMC, peripheral blood mononuclear cells.
 Note: No sample collections for PK, ADA, ██████████, links at the screening visit.
 * Samples to be collected within 10% of nominal time point (e.g., 1 hr ± 6 min, 48 hrs ± 4.8 hrs) for first 48 hours.

¹ Sample to be obtained at Follow-up, unless a new anticancer treatment has been initiated.
² Patients who test positive for ADAs may be requested to supply additional ADA samples.

13.2 Appendix: Response Assessment of Hodgkin and Non-Hodgkin Lymphoma (Lugano Classification)

Response Assessment of Hodgkin and Non-Hodgkin Lymphoma (Lugano Classification)

| Response / Site | PET-CT-Based Response | CT-Based Response |
|--------------------------------------|--|--|
| Complete | Complete metabolic response | Complete radiologic response (all of the following) |
| Lymph nodes and extralymphatic sites | 
 Score 1, 2, or 3* with or without a residual mass on SPS** 
Note: Uptake may be greater than normal mediastinum and/or liver in Waldeyer's ring or extranodal sites with high physiologic uptake or with activation within spleen or marrow (e.g., with chemotherapy or myeloid colony-stimulating factors). In this circumstance, complete metabolic response may be inferred if uptake at sites of initial involvement is no greater than surrounding normal tissue even if the tissue has high physiologic uptake
 | 
 Target nodes/nodal masses must regress to ≤ 1.5 cm in LD No extralymphatic sites of disease |
| Nonmeasured lesion | 
 Not applicable | 
 Absent |
| Organ enlargement | 
 Not applicable | 
 Regress to normal |
| New lesions | 
 None | 
 None |
| Bone marrow | 
 No evidence of FDG-avid disease in marrow | 
 Normal by morphology; if indeterminate, IHC negative |
| Partial | Partial metabolic response | Partial remission (all of the following) |
| Lymph nodes and extralymphatic sites | 
 Score 4 or 5** with reduced uptake compared with baseline and residual mass(es) of any size. At interim, these findings suggest responding disease. At end of treatment, these findings indicate residual disease. | 
 $\geq 50\%$ decrease in SPD of up to 6 target measurable nodes and extranodal sites When a lesion is too small to measure on CT, assign 5 mm \times 5mm as the default value. When no longer visible, 0 \times 0 mm For a node >5 mm \times 5 mm, but smaller than normal, use actual measurement for calculation |

Response Assessment of Hodgkin and Non-Hodgkin Lymphoma (Lugano Classification)

| Response / Site | PET-CT-Based Response | CT-Based Response |
|---|--|---|
| Nonmeasured lesion | 
 • Not applicable | 
 • Absent/normal, regressed, but no increase |
| Organ enlargement | 
 • Not applicable | 
 • Spleen must have regressed by >50% in length beyond normal |
| New lesions | 
 • None | 
 • None |
| Bone marrow | 
 • Residual uptake higher than uptake in normal marrow but reduced compared with baseline (diffuse uptake compatible with reactive changes from chemotherapy allowed). If there are persistent focal changes in the marrow in the context of a nodal response, consideration should be given to further evaluation with MRI or biopsy or an interval scan | 
 • No applicable |
| <hr/> | | |
| No response or stable disease | No metabolic response | Stable disease |
| Target nodes/nodal masses, extranodal lesions | 
 • Score 4 or 5 with no significant change in FDG uptake from baseline at interim or end of treatment | 
 • <50% decrease from baseline in SPD of up to 6 dominant, measurable nodes and extranodal sites; no criteria for progressive disease are met |
| Nonmeasured lesions | 
 • Not applicable | 
 • No increase consistent with progression |
| Organ enlargement | 
 • Not applicable | 
 • No increase consistent with progression |
| New lesions | 
 • None | 
 • None |
| Bone marrow | 
 • No change from baseline | 
 • Not applicable |
| <hr/> | | |
| Progressive disease | Progressive metabolic disease | Progressive disease (requires at least 1 of the following) |
| Individual target nodes/nodal masses | 
 • Score 4 or 5 with an increase in intensity of uptake from baseline and/or | 
 • PPD progression |

Response Assessment of Hodgkin and Non-Hodgkin Lymphoma (Lugano Classification)

| Response / Site | PET-CT-Based Response | CT-Based Response |
|---------------------|--|---|
| Extranodal lesions | 
 New FDG-avid foci consistent with lymphoma at interim or end of treatment assessment | 
An individual node/lesion must be abnormal with:
 
 LDi > 1.5 cm and Increase by $\geq 50\%$ from PPD nadir and An increase in LDi or SDi from nadir 0.5 cm for lesions ≤ 2 cm 1.0 cm for lesions > 2 cm In the setting of splenomegaly, the splenic length must increase by > 50% of the extent of its prior increase beyond baseline (e.g., a 15-cm spleen must increase to > 16 cm). If no prior splenomegaly, must increase by at least 2 cm from baseline New or recurrent splenomegaly |
| Nonmeasured lesions | 
 None | 
 New or clear progression of preexisting nonmeasured lesions |
| New lesions | 
 New FDG-avid foci consistent with lymphoma rather than another etiology (e.g., infection, inflammation). If uncertain regarding etiology of new lesions, biopsy or interval scan may be considered | 
 Regrowth of previously resolved lesions A new node > 1.5 cm in any axis A new extranodal site > 1.0 cm in any axis; if < 1.0 cm in any axis, its presence must be unequivocal and must be attributable to lymphoma Assessable disease of any size unequivocally attributable to lymphoma |
| Bone marrow | 
 New or recurrent FDG-avid foci | 
 New or recurrent involvement |

Abbreviations: 5PS, 5-point scale; CT, computed tomography; FDG, fluorodeoxyglucose; IHC, immunohistochemistry; LDi, longest transverse diameter of a lesion; MRI, magnetic resonance imaging; PET, positron emission tomography; PPD, cross product of the LDi and perpendicular diameter; SDi, shortest axis perpendicular to the LDi; SPD, sum of the product of the perpendicular diameters for multiple lesions.

* A score of 3 in many patients indicates a good prognosis with standard treatment, especially if at the time of an interim scan. However, in trials involving PET where de-escalation is investigated, it may be preferable to consider a score of 3 as inadequate response (to avoid undertreatment). Measured dominant lesions: Up to six of the largest dominant nodes, nodal masses, and extranodal lesions selected to be clearly measurable in two diameters. Nodes should preferably be from disparate regions of the body and should include, where applicable, mediastinal and retroperitoneal areas. Non-nodal lesions include those in solid organs (e.g., liver, spleen, kidneys, lungs), GI involvement, cutaneous lesions, or those noted on palpation. Nonmeasured lesions: Any disease not selected as measured, dominant disease and truly assessable disease should be considered not measured. These sites include any nodes, nodal masses, and extranodal sites not selected as

Response Assessment of Hodgkin and Non-Hodgkin Lymphoma (Lugano Classification)

| Response / Site | PET-CT-Based Response | CT-Based Response |
|-----------------|-----------------------|-------------------|
|-----------------|-----------------------|-------------------|

dominant or measurable or that do not meet the requirements for measurability but are still considered abnormal, as well as truly assessable disease, which is any site of suspected disease that would be difficult to follow quantitatively with measurement, including pleural effusions, ascites, bone lesions, leptomeningeal disease, abdominal masses, and other lesions that cannot be confirmed and followed by imaging. In Waldeyer's ring or in extranodal sites (e.g., GI tract, liver, bone marrow), FDG uptake may be greater than in the mediastinum with complete metabolic response, but should be no higher than surrounding normal physiologic uptake (e.g., with marrow activation as a result of chemotherapy or myeloid growth factors).

** PET 5PS: 1, no uptake above background; 2, uptake \leq mediastinum; 3, uptake $>$ mediastinum but \leq liver; 4, uptake moderately $>$ liver; 5, uptake markedly higher than liver and/or new lesions; X, new areas of uptake unlikely to be related to lymphoma.

Reference: Cheson BD, Fisher RI, Barrington SF, Cavalli F, Schwartz H, Lister TA. Recommendations for initial evaluation, staging, and response assessment of Hodgkin and Non-Hodgkin lymphoma: The Lugano classification. *J Clin Onc* 2014, 32(27):3059-3068

13.3 Appendix: Global Response Score Grading Scales for Modified Severity-weighted Assessment Tool (mSWAT) for CTCL

13.3.1 Skin Scoring

13.3.1.1 Total Body Surface Area (TBSA) Involvement by Skin Disease

The body is divided into 12 regions with pre-assigned percentage (%) total body surface area (TBSA) based on the burn literature. The extent of skin disease in each region is quantified by using the patient's palm to measure the %TBSA involvement within region: patient's palm with 4 fingers (excluding the thumb) is 1% of TBSA. Patient's palm without fingers is 0.5% of TBSA. The patient's palm with 4 fingers is traced on a transparency sheet at the baseline visit, using a permanent marker that will not rub off or smear. The transparency of the patient's palm should be used in all mSWAT assessments during the course of the clinical study. The transparency will be labeled with the patient's study ID number kept in the patient's study file on site. Using the baseline visit transparency of the patient's palm, the Investigator will measure and record the %TBSA for each lesion type within each of the 12 regions.

13.3.1.2 Severity Weighting Factor

The severity weighting factors will be the following:

- 1= patch (flat erythema or erythema with mild infiltration)
- 2=plaque (elevated erythema or erythema with moderate infiltration)
- 4= tumor or ulceration (erythema with fissuring, ulceration or tumor)

Patch is defined as abnormal skin not elevated from normal skin. A plaque is defined as abnormal skin elevated from normal skin by < 5 mm. A plaque elevated \geq 5 mm is a tumor.

13.3.1.3 Calculating Skin Scores

The sum of %TBSA by lesion is derived by summing the %TBSA from all regions affected by the lesion. The sum of %TBSA across lesion types (patches, plaques and tumors) within each region cannot exceed the %TBSA for the region. For example, the %TBSA for the head region is 7%. The sum of %TBSA across lesion types from head can only range from 0-7%. The skin score subtotal by lesion type are derived by multiplying the sum of %TBSA for patches from all regions by 1, sum of %TBS of plaques from all regions by 2, and the sum of %TBSA of tumors or ulcers from all regions by 4. The skin score total is derived from summing the skin score subtotals for patches, plaques and tumors or ulcers. The skin score total is dimensionless with a scale of 0 to 400.

%TBSA for Each Lesion Type Within Each of the 12 Regions

| Region | Percentage TBSA for the region | Percentage TBSA patch (or flat erythema) | Percentage TBSA plaque (or elevated/indurated erythema) | Percentage TBSA tumor/ulceration (or erythema w/fissuring, ulceration) |
|---------------------------|---------------------------------------|---|--|---|
| Head | 7 | | | |
| Neck | 2 | | | |
| Anterior Trunk | 13 | | | |
| Posterior Trunk | 13 | | | |
| Buttocks | 5 | | | |
| Genitalia | 1 | | | |
| Upper Arms | 8 | | | |
| Forearms | 6 | | | |
| Hands | 5 | | | |
| Thighs | 19 | | | |
| Lower Leg | 14 | | | |
| Feet | 7 | | | |
| %BSA by category | 100 | | | |
| Severity Weighting factor | | ×1 | ×2 | ×4 |
| Skin Score subtotal | | | | |

Abbreviations: TBSA, total body surface area; BSA, body surface area

13.3.1.4 Response Definitions

Responses will be determined by the criteria described in the table below. Progression of disease while on treatment should be confirmed by a second assessment 1 to 4 weeks later so that patients who experience a temporary flare of disease due to skin infection or other intercurrent illnesses are not removed from the study prematurely.

| Response | Description |
|---|--|
| Skin | |
| Complete Response (CR) | No evidence of disease; 100% clearance of skin lesions. |
| Partial Response (PR) | ≥50% decrease in skin scores compared to baseline and improvement is maintained for a minimum of 4 weeks |
| Stable Disease (SD) | < 50% decrease in skin scores compared to baseline |
| Progressive Disease (PD) | ≥ 25% increase in skin scores compared to baseline while the patient is actively taking the study drug, or new tumor(s) ≥ 1 cm diameter in skin disease only patient, or ≥ 50% increase in the sum of the products of the greatest diameters of pathologically positive lymph nodes (should be documented by biopsy) compared to baseline while the patient is actively taking the study drug. |
| Relapse | Any disease recurrence in those with complete response. |
| Lymph Nodes (peripheral and central) | |
| CR | All lymph nodes are now ≤ 1.5 cm in greatest transverse (long axis) diameter by method used to assess lymph nodes at baseline or biopsy negative for lymphoma; in addition, lymph nodes that were N ₃ classification and ≤ 1.5 cm in their long axis and > 1 cm in their short axis at baseline, must now be ≤ 1 cm in their short axis or biopsy negative for lymphoma |
| PR | Cumulative reduction > 50% of the SPD of each abnormal lymph node at baseline and no new lymph node > 1.5 cm in the diameter of the long axis or >1.0 cm in the diameter of the short axis if the long axis is 1-1.5 cm diameter |
| SD | Fails to attain criteria for CR, PR, or PD |
| PD | ≥ 50% increase in SPD from baseline of lymph nodes or Any new node > 1.5 cm in the long axis or > 1 cm in the short axis if 1-1.5 cm in the long axis that is proven to be N ₃ histologically or Loss of response: > 50% increase from nadir in SPD of lymph nodes in those with PR |
| Relapse | Any new lymph node > 1.5 cm in the long axis in those with CR proven to be N ₃ histologically. |
| Viscera | |
| CR | Liver or spleen or any organ considered involved at baseline should not be enlarged on physical exam and should be considered normal by imaging; no nodules should be present on imaging of liver or spleen; any post treatment mass must be determined by biopsy to be negative for lymphoma |
| PR | ≥ 50% regression in any splenic or liver nodules, or in measurable disease (SPD) in any organs abnormal at baseline; no increase in size of liver or spleen and no new sites of involvement |
| SD | Fails to attain criteria for CR, PR, or PD |

| Response | Description |
|-----------------|--|
| PD | >50% increase in size (SPD) of any organs involved at baseline or New organ involvement or Loss of response: >50% increase from nadir in the size (SPD) of any previous organ involvement in those with PR |
| Relapse | New organ involvement in those with CR. |
| Blood | |
| CR (a) | B ₀ : Absence of significant blood involvement, <5% of peripheral blood lymphocytes are atypical (Sézary) cells |
| PR (b) | >50% decrease in quantitative measurements of blood tumor burden from baseline in those with high tumor burden at baseline (B ₂) |
| SD | Fails to attain criteria for CR, PR, or PD |
| PD | B ₀ to B ₂ or >50% increase from Baseline and at least 5,000 neoplastic cells/μL, or >50% increase from nadir and at least 5,000 neoplastic cells/μL for those with OR who were originally B ₂ at baseline. |
| Relapse | Increase of neoplastic blood lymphocytes to ≥ B ₁ in those with CR |

SPD = sum of the maximum linear dimension (major axis) x longest perpendicular dimension (minor axis)

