4.1 Study Design

This is a Phase 1, FIH, open-label, dose-escalation (Part 1) and expansion (Part 2) study of ADCT-301 in patients with relapsed and refractory lymphoma. The study will evaluate the safety and tolerability of ADCT-301 as monotherapy, as well as the preliminary activity, PK, pharmacodynamics, and formation of ADAs of ADCT-301 in patients.

For each patient, the study will include a screening period (up to 28 days), a treatment period (until progressive disease, intolerable toxicity, or withdrawal of consent), and a follow-up period to assess disease progression and survival for up to 12 months after the last dose of study drug. The total study duration will be dependent on overall patient tolerability to the study drug and response to treatment. It is anticipated that the entire study (Parts 1 and 2) could last approximately 3 years from first patient treated to last patient completed.

In Part 1, patients will receive ADCT-301 administered as a 1-hour IV infusion on Day 1 of each 3-week (21-day) cycle. If ADCT-301 is well tolerated after the first cycle, the infusion duration may be shortened to 30 minutes for subsequent cycles at the Investigator's discretion.

The first patient at each dose level will be monitored for any AEs for 7 days before proceeding with dosing for the second patient.

The initial dose level for Part 1 will be 3 µg/kg (Dose Level 1). The highest allowed dose will be 300 µg/kg. The MTD will be the highest safe dose that has at least a 60% probability that the dose-limiting toxicity (DLT) rate is < 30%.

After discontinuation of treatment, patients without documented objective disease progression will be followed until progression of disease or initiation of new anticancer therapy for up to 12 months. All patients will be followed for survival (by telephone contact or retrospective chart review) until a new anticancer therapy is initiated or for up to 12 months after treatment discontinuation.

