5.1.6 Long-term Follow-up

Patients who discontinue treatment for any reason other than objective disease progression will continue to be followed with scans approximately every 12 weeks from the last tumor assessment until disease progression, or initiation of new anticancer treatment. If a patient discontinues treatment for a hematopoietic stem cell transplant, the frequency of imaging will be as per the transplant center standard of care.

After documentation of disease progression or start of new anticancer treatment, patients will be contacted by telephone approximately every 12 weeks for up to 12 months after the last dose of study drug to collect survival information.

Blood Sample Collection and Adverse Event Monitoring During Long-Term Follow-up

For all patients, PK and ADA blood sample collection will be performed 12 weeks (\pm 1 week) following the last dose of ADCT-301, unless a new anticancer treatment has been initiated.

Patients who test positive for ADAs may be requested to supply additional ADA samples.

For all patients, collection of AEs and SAEs will continue for 12 weeks after the last dose of study drug or initiation of new anticancer treatment (see [Section 7.3.2.2](#)).

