13.3.2 Global Response Score

The individual component scores for skin, nodes, blood, and viscera are incorporated into the definition of the Global Response Score (see table below).

| Global Score | Definition | Skin | Nodes | Blood | Viscera |
|--------------------------|---|-------------|--|--------------|----------------|
| Complete Response (CR) | Complete disappearance of all clinical evidence of disease | CR | All categories have CR/noninvolved (NI) | | |
| Partial Response (PR) | Regression of measurable disease | CR | All categories do not have a CR/NI and no category has a PD | | |
| | | PR | No category has a PD and if any category involved at baseline, at least one has a CR or PR | | |
| Stable Disease (SD) | Failure to attain CR, PR, or PD representative of all disease | PR | No category has a PD and if any category involved at baseline, no CR or PR in any | | |
| | | SD | CR/NI, PR, SD in any category and no category has a PD | | |
| Progressive Disease (PD) | Progressive disease | | PD in any category | | |
| Relapse | Recurrence disease in prior CR | | Relapse in any category | | |

References:

Olsen EA, S Whittaker, Kim YH, Duvic M, Prince HM, Lessin SR, et al. Clinical end points and response criteria in mycosis fungoides and Sézary Syndrome: a consensus statement of the International Society for Cutaneous Lymphomas, the United States Cutaneous Lymphoma Consortium, and the Cutaneous Lymphoma Task Force of the European Organisation for Research and Treatment of Cancer. *J Clin Oncol* 2011; 29(18):2598-2607.

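### In CTCL, skin partial responders have no loss-of-response rule from nadir, and skin-score progression counts only on drug, so DOR, and PFS after skin PR or off drug, may run too long

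*Protocol*

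**What the plan says.** Protocol 8.6.1.2 and 8.6.1.4 take the progression date of CTCL patients from the Global Response Score criteria in Appendix 13.3. SAP 4.9 uses the investigator's evaluation on the same scales and adds clinical progression from the end-of-treatment or study disposition page.

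The response table in Protocol 13.3.1.4 sets these rules:

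- **Skin.** PR is a fall of at least 50% from baseline, held for at least 4 weeks. SD is "< 50% decrease in skin scores compared to baseline", with no upper limit. PD by score is a 25% or greater "increase in skin scores compared to baseline while the patient is actively taking the study drug". PD can also come from a new tumor of at least 1 cm in a patient with skin disease only, or from node growth of at least 50% over baseline on drug. Relapse applies to complete responders only.
- **Nodes.** PD includes more than a "50% increase from nadir in SPD of lymph nodes in those with PR".
- **Viscera.** PD includes more than a "50% increase from nadir in the size (SPD) of any previous organ involvement in those with PR".
- **Blood.** PD includes more than a "50% increase from nadir and at least 5,000 neoplastic cells" per microlitre, for responders who were B2 at baseline.

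In Protocol 13.3.2, skin SD together with "CR/NI, PR, SD in any category and no category has a PD" gives a global score of SD.

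After treatment stops, Protocol 4.1 says that "patients without documented objective disease progression will be followed until progression of disease or initiation of new anticancer therapy for up to 12 months". Under 5.1.6 they are "followed with scans approximately every 12 weeks from the last tumor assessment until disease progression" or the start of new treatment. Protocol 5.1.2 and footnote 8 of 13.1.1 name mSWAT as the post-screening method when CTCL is limited to the skin, with imaging only on clinical grounds.

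SAP 4.9.2 and 4.9.4 censor at the last valid assessment if no event has occurred before new anticancer therapy or the cut-off.

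**The concern.** Skin is the only one of the four compartments whose partial responders have no loss-of-response rule measured from nadir. It is also the only one whose score-based PD rule is tied to being on drug. A skin partial responder can regrow to the full baseline score, or to just under 125% of it, and still be skin SD. With no PD elsewhere, the global score is SD too. No DOR or PFS event is then recorded, although the response has been lost.

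Off drug the gap is wider. Follow-up for progression continues, and for skin-limited disease the named measure is mSWAT, yet no rise in that score can by itself be PD for a patient who is not in CR.

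The event then comes late, or the patient starts new therapy and is censored at the last valid assessment. Such censoring is likely to be informative, because regrowth is a natural reason to start new therapy. In either case the Kaplan-Meier estimates for these patients are too favourable.

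**Working it through.** The plan states no figure to reproduce here, so the check is threshold arithmetic on the protocol's own cut-offs.

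**Inputs** (Protocol 13.3.1.3 and 13.3.1.4): skin PR needs a nadir N of at most 0.50 × baseline B. Score-based skin PD needs at least 1.25 × B, on drug. Node and visceral loss of response needs more than 1.5 × nadir. The skin score runs from 0 to 400.

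**Step 1, on-drug rise needed.** The fold rise from nadir is 1.25B / N. With B = 100:

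| Nadir | Score for PD now | Rise from nadir | Trigger if more than 1.5 × nadir were used |
|---|---|---|---|
| 50 | 125 | 125/50 = 2.5-fold (150%) | 75 |
| 25 | 125 | 125/25 = 5-fold (400%) | 37.5 |
| 10 | 125 | 125/10 = 12.5-fold (1150%) | 15 |

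The deeper the response, the larger the regrowth that goes uncounted. The last column borrows the node and visceral rule only to show scale.

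**Step 2, ceiling.** 1.25B exceeds 400 when B > 400/1.25 = 320. Above that baseline, score-based PD cannot be reached even on drug. This is an extreme case: with the highest lesion weight of 4, a score of 320 needs 320/4 = 80% of body surface involved.

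**Step 3, off drug.** The score limb of PD does not apply, so there is no threshold. At assessments every 12 weeks over at most 12 months, 52/12 gives about four assessments at most. At none of them can the score alone give PD for a patient not in CR.

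**Step 4, why no delay in weeks is given.** Under exponential regrowth, the extra growth before an event is log2(125 / trigger) doublings. For a trigger of 1.5 × nadir this is:

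- nadir 50: log2(125/75) = 0.74
- nadir 25: log2(125/37.5) = 1.74
- nadir 10: log2(125/15) = 3.06

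The documents give no doubling time. At assumed values of 6 to 24 weeks, the result runs from 0.74 × 6 = 4.4 weeks to 3.06 × 24 = 73.4 weeks, before visits are applied. It also depends on the trigger. If the trigger were nadir plus half of baseline, the nadir-10 case would have a trigger of 60 and log2(125/60) = 1.06 doublings instead of 3.06. The documents fix neither assumption, so no delay is claimed.

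**The case against.** The strongest reply is that other routes to an event exist. A new tumor of at least 1 cm counts in skin-only patients with no on-drug condition, and under 13.3.1.2 a plaque raised to 5 mm is a tumor. PD in nodes, viscera or blood counts, as does death. The SAP also counts clinical progression at end of treatment or end of study. These routes stand and narrow the point. None of them is a skin-score rule, however. Clinical progression depends on a disposition-page entry with no skin threshold, and it is absent from the protocol's DOR definition.

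A threshold measured from baseline is also a coherent definition of PFS, and the appendix cites published consensus criteria that cannot be examined here. The inconsistency is therefore mainly about DOR, and it rests on the compartments of this table differing from each other, not on any departure from the source. SAP 4.9.1 lists mSWAT by visit, and 4.9.2 allows a DOR subgroup by disease subtype. A careful reader could thus see lost skin responses, but the estimates themselves would not reflect them.

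Two cautions about a remedy also stand. The confirmation 1 to 4 weeks later in 13.3.1.4 applies only on treatment, so counting off-drug rises could pick up temporary flares. Off-drug mSWAT is explicit only for skin-limited disease; otherwise 5.1.6 speaks of scans.

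A reader might infer more than the documents support:

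- That skin PD or Relapse is not an event at all, because SAP 4.9.2 and 4.9.4 mention radiographic or clinical progression. SAP 4.9 already brings in the Global Response Score, and 4.9.1 groups relapse with PD.
- That progression cannot be recorded off drug. The routes above show that it can.
- That ORR is affected. It depends on best response, which this gap does not change.

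**Conclusion.** The point holds as a minor one. Applied as written, the plan can leave a skin partial responder whose disease has fully regrown as SD, with no DOR or PFS event. Off drug, the skin score alone cannot give PD for any CTCL patient not in CR. What the documents support numerically is the 2.5-, 5- and 12.5-fold rises and the unreachable threshold above a baseline of 320. They do not support a delay in weeks or a shift in any median.

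The conclusion assumes that investigators apply the table literally and that no other route to an event comes first. Apart from the scale ceiling, patients on drug who never reached skin PR are not affected. The endpoints are secondary, SAP 4 plans no hypothesis testing, and the number of CTCL patients is not given.

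**What to change.** Keep the investigator-assessed DOR and PFS as planned, with no change to treatment decisions. Add to SAP 4.9.2 and 4.9.4 a pre-specified supplementary derivation for CTCL patients with recorded mSWAT scores:

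1. Apply the skin-score PD limb without the on-drug condition.
2. For patients in skin PR, add a loss-of-response criterion from nadir parallel to the rule of more than 50% in the other compartments. Fix a minimum absolute rise before analysis, so that small changes near a low nadir do not count.
3. For off-drug rises, use a second recorded assessment as confirmation where one exists, and flag unconfirmed rises.
4. Limit the off-drug part to patients with mSWAT in follow-up, and report how many have it.

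The protocol's skin rule should also be reconciled with the nadir rules of the other compartments and with off-drug follow-up.

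The cost is a few SAP sentences and a small programmed derivation from scores already planned for collection and listing. The downsides are two reported versions of CTCL DOR and PFS, a derived version that is somewhat shorter, and some risk of counting off-drug flares.

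Naming Relapse as an event in SAP 4.9.2 and 4.9.4, and aligning the reference to scans in Protocol 5.1.6 with the mSWAT footnote, are optional clarifications outside this point.
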